## **Abstract**

Nearly 30 million Americans have type 2 diabetes (T2DM), a disorder with serious health consequences such as cardiovascular and renal disease. Almost 90 million more have prediabetes, with estimates of 8 million undiagnosed (CDC, National Diabetes Statistics Report). Insulin resistance (IR) is a precursor to prediabetes and T2DM (NIDDK, Insulin resistance and prediabetes). There is evidence of IR in those with short sleep [normal weight (Matthews et al., 2012); obese (Liu, Kushida, & Reaven, 2013)]. The risk for developing diabetes in persons with difficulty in maintaining sleep is 1.84 times the risk of diabetes in those who do not have sleep issues which is very similar to the relative risk detected from another commonly recognized risk factor-- family history of diabetes (1.7-2.3) (Reutrakul & Van Cauter, 2014). For this pilot study we will recruit 20 young adults, accounting for attrition, age 18-25 years who have elevated HOMA-IR (based on established cut points), short sleep duration (< 7 hrs./night) and obesity (BMI  $\geq$  30) (another risk factor for IR), and use a two-group, pre-test/post-test experimental design including objective actigraphy data for sleep. The specific aims are to: 1) evaluate the feasibility and acceptability of a tailored intervention to extend sleep duration (SLEEP-Extend), 2) determine changes in sleep duration after SLEEP-Extend intervention, 3) evaluate IR levels before and after SLEEP-Extend, and 4) explore the potential mediators of diet and physical activity between sleep duration and IR. Screening data will include measures of sleep duration, age, IR and BMI. After enrollment, baseline data will include pre-test of sleep hygiene knowledge, self-report measures of diet and physical activity as well as one week of objective monitoring of sleep using actigraphy. After all baseline data are collected, participants will be randomly assigned to group. The SLEEP-Extend intervention group will receive sleep hygiene education and instructions to increase time in bed by one hour total each night for an additional 4 weeks. The attention control group will receive education on safety practices in an urban environment. Both groups will receive the sleep hygiene post-test immediately after the intervention, and they will continue with actigraphy monitoring for 4 weeks. After the 4-week intervention period, both groups will have measures of IR, BMI, final post-test of sleep hygiene knowledge, self-reported diet and physical activity, and an exit interview, and actigraphy data will be downloaded. This study will examine whether an intervention to extend sleep will result in behavior change to increase sleep duration and improve IR.

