### **PROCEDURES:**

For interested participants, initial screening on the telephone for age, average sleep duration, and BMI will be done and if eligible, an appointment will be set and instructions for fasting (participant will be instructed to not eat or drink anything for 8 hours) for the screening visit (Visit #1). At Visit #1 we will obtain written informed consent that will include information on screening process: eligibility of IR (from blood sample) and height and weight measures will be obtained for BMI. Blood samples will be analyzed within one week. If HOMA-IR level is elevated in these obese individuals with short sleep, then they will be contacted and 2 additional appointments will be made. If they do not have elevated HOMA-IR levels, the researcher will call and thank them for their interest and let them know they are not eligible. Visit #2, baseline (BL) visit, will be within 2 weeks of obtaining initial blood result and consent will be confirmed (for enrollment in the study) and other BL data will be collected. Also, participants will be given a sleep diary to complete and an actigraphy watch to wear for one week for BL sleep assessment. During visit #3 (intervention visit) which is one week after BL visit, the BL actigraphy data will be downloaded and the participant instructed to continue to wear the watch for 4 more weeks. Randomization to groups will occur, and each group will receive the appropriate intervention content for the group. Immediately after the intervention, the appropriate knowledge post-test will be given according to assigned group. The SLEEP-Extend group will decide on when they are able to extend their TIB. After 2 more weeks both groups will receive a telephone call to reinforce content and answer questions about extending TIB and sleep hygiene for SLEEP-Extend group and safety information in the control group. At this telephone call the final appointment will be set for 2 weeks later and for a reminder to come in fasting. Visit #4 is the at the end of the 4-week intervention period, and data collection will include drawing of blood samples, downloading of actigraphy data with return of the watch and daily sleep diary and completing responses to standard questionnaires. To strengthen the design, we have made time spent with both groups similar throughout the study. All participants will

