receive \$20 after one week of baseline data. At the end of the study, all participants will receive an additional \$30, a certificate of appreciation and a booklet on Healthy Sleep (NHLBI, 2011). Any participants that are noted to have additional risk factors for T2DM will be provided educational material on reducing T2DM risk factors and the suggestion made to follow up with a physician. After serum blood values are analyzed, all participants will be sent a letter with their glucose, insulin and HOMA-IR information along with a description of these values and recommendation for physician follow up. The principal investigator is a registered nurse who will collect the data and administer the sleep intervention. Standard universal precautions will be used during blood draws. Additionally, a GRA, also a registered nurse, will assist with data collection.

**Sample size:** A target sample size of 10 in the SLEEP-Extend group and 10 in the control will be used for this feasibility study (accounting for 20% attrition) given the need for a serum blood test as part of screening a number of participants to meet strict eligibility criteria. Participants will be randomly assigned to either the control or SLEEP-Extend group using a table of random numbers.

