### **Informed Consent Process and Visit Details**

1. Potential subjects will contact the PI using contact information from recruitment materials
2. The PI will explain the purpose of the study and conduct initial screening for eligibility by telephone. Potential subjects will be informed that the intent of the study is to examine how sleep behaviors affect risks for developing type 2 diabetes and to determine their willingness to participate in a 4-week home-based program (intervention) focused on personal sleep behaviors.
3. The initial telephone screening will include:
  - a. Obtain Consent (verbal)

- b. Asking age (must be 18-25 years old) and if the subject has the ability to read and write English and their self-reported height and weight for BMI calculation;
  - c. Reviewing exclusion criteria [night shift worker; sleep disorder diagnosis; medical diagnosis of diabetes or pre-diabetes; currently pregnant or lactating or with history of gestational diabetes; actively participating in a weight loss program; hospitalization in past 3 months for any medical or psychiatric condition; having a major chronic illness (e.g. cancer, Lupus)]; and
  - d. Reviewing initial inclusion criteria to determine potential eligibility:
    - i. Self-reported short sleep duration of < 7 hours/night
    - ii. Asking if they are willing to participate in a 4-week program focusing on sleep behavior
    - iii. Administration of the Insomnia Severity Index (valid and reliable) to determine sleep quality (Inclusion criteria includes good quality sleep and is total score of < 15)
  - e. If the subjects do not meet the initial inclusion criteria, they will be thanked for their interest and told they are not eligible for the study.
  - f. If a subject meets initial inclusion requirements:
    - i. An appointment will be set up at a mutually convenient date and time, within morning hours to be able to obtain a fasting blood sample and baseline actigraphy data for sleep duration and nighttime oxygen saturation and will take place in a private room located on the university campus.
    - ii. Instructions will be given for fasting prior to this first appointment (subject will be instructed to not eat or drink anything for 10 hours prior to the first appointment). The first appointment is Visit #1 (Screening Visit)

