- e. After one week of baseline actigraphy and pulse oximetry monitoring, the subject will return the actigraph and pulse oximeter and data will be downloaded and analyzed for sleep duration and oxygen saturation respectively. The researcher or GRA will access sleep diary information from the SleepBot app by taking a screen-shot of the data and printing it. Sleep diary info on the screen-shot will be deleted and only a paper version of the sleep diary will be retained. If the subject used a paper sleep diary, then it will be returned to the researcher for analysis.
- f. If the subject's average sleep duration is not below 7 hours per night or their insulin resistance level does not meet the inclusion criteria (HOMA-IR is a measure of insulin

resistance and needs to be  $\geq 2.1$  in order to meet inclusion criteria), or if their oxygen desaturation index is  $\geq 5$ /hour they will be thanked for their interest and told they are not eligible for the study. Additionally, if the subject's oxygen desaturation index is  $\geq 5$ /hour, they will be instructed to follow up with a health provider for assessment of possible OSA.

- g. If the subject's average sleep duration is less than 7 hours per night and their HOMA-IR meets inclusion criteria ( $\geq 2.1$ ) and their oxygen desaturation index is  $< 5$ /hour, then the subject will be scheduled for their study enrollment visit (Visit #2) to collect questionnaires/surveys. Subjects will be given \$10 after the screening visit.
5. Visit #2 (Study Enrollment Visit): This visit is done as soon as possible following screening. The researcher or GRA will meet the subject in a private room located on the university campus. The study enrollment visit for all subjects includes randomization to the treatment or control group and completion of:
  - a. Researcher-developed demographic/subject characteristics questionnaire
  - b. Baecke physical activity questionnaire
  - c. Dietary Screener questionnaire
  - d. Meal Timing questionnaire
  - e. Perceived Stress Scale
  - f. Sleep Hygiene Index questionnaire
  - g. Control group only: an investigator-developed safety practices questionnaire
  - h. Each subject will be asked to wear the actigraphy watch continuously for 4 additional weeks and complete daily sleep diary for 4 additional weeks (as previously discussed).
  - i. The intervention will be administered as follows

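### Assignment is by a table of random numbers, with no allocation concealment and no independent holder of the sequence, while the staff who recruit also treat

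*Combined protocol and SAP*

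**What the plan says.** The Sample size paragraph under PROCEDURES gives the method: "Participants will be randomly assigned to either the control or SLEEP-Extend group using a table of random numbers". No section says who prepares the sequence, who holds it, when it is read, or how it is kept from the people enrolling participants.

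The staffing is as follows.

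- Telephone contact, item 2 of Informed Consent Process and Visit Details: "The PI will explain the purpose of the study and conduct initial screening for eligibility by telephone".
- Data and delivery, under PROCEDURES: "The principal investigator is a registered nurse who will collect the data and administer the sleep intervention".
- Second staff member, same place: "Additionally, a GRA, also a registered nurse, will assist with data collection".
- Items 4 and 5 of Informed Consent Process and Visit Details have the researcher or the GRA obtain written consent, handle the downloaded eligibility data, and meet the participant at the visit that includes randomisation.

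The time of assignment is given in three places. The Abstract says "After all baseline data are collected, participants will be randomly assigned to group". PROCEDURES puts it at Visit #3, one week after the baseline visit: "Randomization to groups will occur, and each group will receive the appropriate intervention content for the group". Informed Consent Process and Visit Details puts it at Visit #2, alongside the baseline questionnaires: "The study enrollment visit for all subjects includes randomization to the treatment or control group and completion of". In that second schedule the visit date is loose: "This visit is done as soon as possible following screening".

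**The concern.** Randomisation protects a comparison only if those who decide who enters, and when, cannot foresee the next arm. Here the same one or two people recruit, consent, check eligibility, book, randomise and treat, and no one else is given a part in assignment. If the plan is followed as written, one of them applies the table.

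The intervention depends on a participant's willingness and freedom to spend longer in bed, and staff form a view of both before assignment. If more willing candidates went to SLEEP-Extend, even without intent, sleep duration, adherence and retention would look better in that arm. H1 and H2 under Objectives are both between-group comparisons. The Introduction presents the control group as a strength of the design and wants the results to be the foundation for a larger study. Motivation is not among the listed measures, so an imbalance in it could be neither seen nor adjusted for.

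**Working it through.** No stated figure depends on concealment, so there is none of the plan's own to reproduce. The check has three parts.

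**1. Where discretion remains.**

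- Left to staff: judging willingness to extend time in bed (an inclusion criterion), accepting the self-reported exclusions, timing appointments, and the effort spent keeping a hesitant candidate.
- Not left to staff: HOMA-IR of at least 2.1, actigraphy sleep below 7 hours, and a desaturation index below 5 per hour. These are numeric rules applied after consent.
- Partly constrained: in the PROCEDURES schedule, the baseline visit falls within 2 weeks of the blood result and randomisation one week later. The other schedule has no such window.

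**2. Illustrative size if the next arm were known.** Inputs: 20 participants (from the plan), simple 1:1 randomisation, a standard-normal trait, and a queue of k eligible people. With probability f, staff book the highest-trait person for SLEEP-Extend or the lowest-trait person for control; otherwise booking is first come, first served. Queue length and f are assumptions. There were 20,000 replicates per setting. Mean between-arm difference in the trait, in SD:

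| Queue | f = 0.25 | f = 0.50 | f = 1.00 |
|---|---|---|---|
| 1 | 0 | 0 | 0 |
| 2 | 0.29 | 0.57 | 1.13 |
| 3 | 0.40 | 0.77 | 1.38 |

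A rerun agreed to within 0.01. For scale, the chance SD of this difference with 20 people and no steering is about 0.46.

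**3. What a shift would do to a test.** Assume a shift of d SD carries through fully to the outcome and there is no true effect. A two-sided 5% t-test with n per arm has noncentrality d × √(n/2) on 2n − 2 degrees of freedom. With n = 10 and d = 0.5, that is 0.5 × √5 = 1.118 on 18 degrees of freedom, which gives rejection in 18.5% of trials.

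| d | 10 per arm | 8 per arm (20 × 0.8 = 16 completers) |
|---|---|---|
| 0.25 | 8.3% | 7.5% |
| 0.50 | 18.5% | 15.4% |
| 0.75 | 35.5% | 28.7% |

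**A related point on predictability.** An unrestricted table gives exactly 10:10 with probability C(20,10)/2^20 = 184,756/1,048,576 = 0.176, so reaching 10 per arm needs some rule that the plan does not state. Suppose the list is forced to 10:10 and past assignments are known, as they are to a PI who delivers the intervention. Guessing the arm that is behind is then right 10 + (4^10/184,756 − 1)/2 = 12.3 times in 20 on average, against 10 by chance, and about the last 1.8 assignments are certain. If the table is used until one arm is full, about 3.5 assignments are forced on average.

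**The case against.** A reader might infer that the table is open and that staff see the coming arm before deciding whom to book. The documents do not support that. They name a generation method and are silent on who reads the table, when, and whether a list exists in advance. Silence is not a described procedure.

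A reader might also take the loose date of Visit #2 as freedom to choose who goes next. On its face the wording asks staff not to delay, and the PROCEDURES schedule ties dates to each person's blood result. Willingness and exclusions are reviewed at the first telephone call, well before assignment. Steering at that point would mean guessing which slot someone will fill after unknown screen failures.

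The simulation needs a standing queue of fully eligible people, which may seldom exist. The Introduction reports that almost 20% of 32 short sleepers had insulin resistance and half of those were obese: 0.2 × 32 = 6.4, half of which is about 3 people. The trait is hypothetical, no link to sleep duration or HOMA-IR is given, and the 0.29 SD case is smaller than the chance SD of 0.46. Work hours are collected and may serve as a covariate, so part of schedule flexibility could be adjusted for.

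All of this stands, and it limits how much can be claimed. It does not supply a concealment step or an independent holder. Booking order and retention effort stay with the treating staff, and motivation stays unmeasured.

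**Conclusion.** The concern holds as a gap in protection, not as demonstrated bias. No concealment and no independent holder are described, the people who recruit also treat, and selection into arms cannot be ruled out. The numeric entry criteria and the visit windows in PROCEDURES reduce the opportunity without closing it.

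The range of about 0.3 to 1.4 SD is illustrative. It rests on a visible next arm, a constant queue of 2 or 3, and 25% to 100% of bookings being steered. It describes an assumed trait, not an outcome, and is 0 when only one person is waiting. The rejection rates further assume that the shift carries through fully to the outcome. For a 20-person feasibility study this is something the sponsor should change because the remedy is cheap. It does not invalidate the design.

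**What to change.** Replace the randomisation sentence in the Sample size paragraph with text such as:

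*The allocation sequence will be generated before enrolment and concealed from the PI and the GRA, either in the randomisation function of the study database or in sequentially numbered, opaque, sealed envelopes prepared by a colleague with no role in recruitment, data collection or intervention. Each assignment will be released only after eligibility is confirmed, all baseline measures including questionnaires are complete, and the participant's ID, date and time are logged.*

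Keep the log as a study record. State with the sequence whatever restriction is used to reach 10 per arm, and keep its details from the PI and GRA.

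Reconcile the randomisation visit (Visit #3 in PROCEDURES, Visit #2 in Informed Consent Process and Visit Details) with the Abstract's statement that assignment follows all baseline data. Confirming eligibility alone is not a sufficient trigger. In the Visit #2 schedule, randomisation shares a visit with the baseline questionnaires and their order is not given.

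Cost: about an hour of set-up. If envelopes are used, 20 are needed if 20 is the number randomised. If 20 is the number completing, 26 are needed (10/0.8 = 12.5, rounded up to 13 per arm). Visits, measures and sample size do not change.

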### **Alternative Strategies**

Although studies have shown the efficacy of extending time in bed as a method to increase sleep duration, it may be difficult for participants to increase TIB by one hour all at once immediately at the beginning of the 4-week intervention period. An alternative strategy would be to have participants slowly increase their TIB in 15 min increments over a 1-week period which may be more manageable for the participant (not too big or too small) but not to exceed a total of one hour each night. One study (unpublished work) found that using this strategy for a sleep extension intervention was efficacious and reported reduction in IR in their obese adults (Rogers et al, 2013).

### **Informed Consent Process and Visit Details**

1. Potential subjects will contact the PI using contact information from recruitment materials
2. The PI will explain the purpose of the study and conduct initial screening for eligibility by telephone. Potential subjects will be informed that the intent of the study is to examine how sleep behaviors affect risks for developing type 2 diabetes and to determine their willingness to participate in a 4-week home-based program (intervention) focused on personal sleep behaviors.
3. The initial telephone screening will include:
  - a. Obtain Consent (verbal)

- b. Asking age (must be 18-25 years old) and if the subject has the ability to read and write English and their self-reported height and weight for BMI calculation;
  - c. Reviewing exclusion criteria [night shift worker; sleep disorder diagnosis; medical diagnosis of diabetes or pre-diabetes; currently pregnant or lactating or with history of gestational diabetes; actively participating in a weight loss program; hospitalization in past 3 months for any medical or psychiatric condition; having a major chronic illness (e.g. cancer, Lupus)]; and
  - d. Reviewing initial inclusion criteria to determine potential eligibility:
    - i. Self-reported short sleep duration of < 7 hours/night
    - ii. Asking if they are willing to participate in a 4-week program focusing on sleep behavior
    - iii. Administration of the Insomnia Severity Index (valid and reliable) to determine sleep quality (Inclusion criteria includes good quality sleep and is total score of < 15)
  - e. If the subjects do not meet the initial inclusion criteria, they will be thanked for their interest and told they are not eligible for the study.
  - f. If a subject meets initial inclusion requirements:
    - i. An appointment will be set up at a mutually convenient date and time, within morning hours to be able to obtain a fasting blood sample and baseline actigraphy data for sleep duration and nighttime oxygen saturation and will take place in a private room located on the university campus.
    - ii. Instructions will be given for fasting prior to this first appointment (subject will be instructed to not eat or drink anything for 10 hours prior to the first appointment). The first appointment is Visit #1 (Screening Visit)
4. Visit #1 (screening visit) will include obtaining blood samples to calculate insulin resistance, 2 consecutive nights of pulse oximetry and one week of baseline sleep duration using Actigraphy monitoring. The researcher will meet the subject in a private room located on the university campus and will conduct explanation of consent.
- a. The researcher or GRA will obtain written informed consent and a copy provided to the subject.
  - b. The researcher will confirm the subject has not had anything to eat or drink in the past 10 hours
  - c. A registered nurse (either the researcher or GRA) will obtain the following
    - i. Blood sample will be obtained using standard protocol with universal precautions to obtain fasting serum blood glucose and plasma insulin levels. These levels will be used to calculate insulin resistance. A registered nurse will pierce the subject's skin (usually in a vein located on the inside middle part of the arm) with a very small needle and take the blood into a small tube. This method of taking blood is called a venipuncture. The total amount of blood drawn is about 5 ml or 1 teaspoon. During the blood draw, the subject will feel a pinch that lasts several seconds when the blood sample is taken. The subject may have pain, dizziness, bleeding, or bruising at the site of the blood draw. There is a slight risk of infection and scarring at the site of the blood draw. However, the registered nurse will use proper technique while taking the blood sample in order to reduce unwanted effects.
    - ii. After obtaining the blood sample, the subject will be offered a light snack (granola bar, crackers or cookies) to eat and water or juice to drink.

- iii. Subject blood samples will be labeled using a unique identification number and will be stored in a secure laboratory at Emory University until they can be analyzed by Cardiovascular Specialty Laboratories, Inc. in Atlanta, GA. The blood samples will be destroyed by Cardiovascular Specialty Laboratories, Inc. once analysis of blood levels is completed. IBC protocol submitted and approval is pending.
- d. The researcher or GRA will obtain and instruct in the following:
  - i. Subject height (using a stadiometer) without shoes
  - ii. Subject weight (using a calibrated scale) in light clothing and no shoes
  - iii. Subject body fat analysis (using a hand-held, non-invasive calibrated scale) (Omron Body Logic Pro, Omron Healthcare, Inc., Vernon Hills, IL
  - iv. Instructions for wearing the wrist actigraph [wear the wrist actigraph (Motionlogger, AMI, Ardsley, NY) continuously for 1 week (device is water resistant; however, subjects will be instructed to remove for showering or other activities requiring hands to be submerged in water) to monitor activity and rest cycles throughout the week and weekend for a total of 1 week]. The researcher or GRA will answer any questions the subject has and will provide contact information if the subject has any questions or problems with the actigraph or skin irritation around the actigraph.
  - v. Instructions for completing a daily sleep diary. If the subject agrees, they will download a smart phone app called SleepBot-Sleep Cycle Alarm which is compatible with Android and iPhone (and is free) and will allow subject to record the following information. If the subject does not wish to use the SleepBot-Sleep Cycle Alarm app, they will record the following information in a paper sleep diary:
    - 1. Time they go to bed
    - 2. Time they wake up
    - 3. Any instances of waking up and/or getting out of bed during the night.
  - vi. Instructions for wearing the pulse oximetry (WristOx2; Nonan Medical Inc., Plymouth, MN). This is a non-invasive device that is worn on the wrist along with a finger sensor that will assess oxygen saturation levels during the night. A decrease in oxygen saturation levels could signify obstructive sleep apnea (OSA). A desaturation index of  $\geq 5$ /hour potentially indicates OSA. We will exclude persons with potential OSA because OSA can alter glucose levels and lead to insulin resistance. This device will be worn on the opposite wrist from the actigraphy monitor and will only be worn during the night for 2 nights during the one week of baseline screening data collection. The researcher or GRA will answer any questions the subject has and will provide contact information if the subject has any questions or problems with the pulse oximeter.
- e. After one week of baseline actigraphy and pulse oximetry monitoring, the subject will return the actigraph and pulse oximeter and data will be downloaded and analyzed for sleep duration and oxygen saturation respectively. The researcher or GRA will access sleep diary information from the SleepBot app by taking a screen-shot of the data and printing it. Sleep diary info on the screen-shot will be deleted and only a paper version of the sleep diary will be retained. If the subject used a paper sleep diary, then it will be returned to the researcher for analysis.
- f. If the subject's average sleep duration is not below 7 hours per night or their insulin resistance level does not meet the inclusion criteria (HOMA-IR is a measure of insulin

resistance and needs to be  $\geq 2.1$  in order to meet inclusion criteria), or if their oxygen desaturation index is  $\geq 5$ /hour they will be thanked for their interest and told they are not eligible for the study. Additionally, if the subject's oxygen desaturation index is  $\geq 5$ /hour, they will be instructed to follow up with a health provider for assessment of possible OSA.

- g. If the subject's average sleep duration is less than 7 hours per night and their HOMA-IR meets inclusion criteria ( $\geq 2.1$ ) and their oxygen desaturation index is  $< 5$ /hour, then the subject will be scheduled for their study enrollment visit (Visit #2) to collect questionnaires/surveys. Subjects will be given \$10 after the screening visit.
5. Visit #2 (Study Enrollment Visit): This visit is done as soon as possible following screening. The researcher or GRA will meet the subject in a private room located on the university campus. The study enrollment visit for all subjects includes randomization to the treatment or control group and completion of:
  - a. Researcher-developed demographic/subject characteristics questionnaire
  - b. Baecke physical activity questionnaire
  - c. Dietary Screener questionnaire
  - d. Meal Timing questionnaire
  - e. Perceived Stress Scale
  - f. Sleep Hygiene Index questionnaire
  - g. Control group only: an investigator-developed safety practices questionnaire
  - h. Each subject will be asked to wear the actigraphy watch continuously for 4 additional weeks and complete daily sleep diary for 4 additional weeks (as previously discussed).
  - i. The intervention will be administered as follows
    - i. Intervention Group (SLEEP-Extend intervention): The SLEEP-Extend intervention consists of two components:
      1. One education session (5-10 minutes) consisting of strategies for sleep hygiene which is the routine for going to sleep (an investigator-developed brochure and information based on recommendations from the American Academy of Sleep Medicine and the National Sleep Foundation will be given and reviewed with the subject)
      2. Instructions on extending time in bed by at least one hour but can be up to 2 hours total per night for 4 weeks which can be accomplished by either going to bed earlier or staying in bed later (subject will decide what works best for them).
    - ii. Control group:
      1. One educational session (5-10 minutes) consisting of safety practices used for an urban environment (a safety brochure and safety information developed by the Emory Police department will be given and reviewed with the subject)
  - j. At the end of Visit #2, all subjects will receive \$20.
6. Follow up contact after Visit #2: The subject will be contacted weekly (via text or phone depending on their preference) to reinforce content and answer any questions. Another appointment will be made for Visit #3 (end of the 4 week intervention period) and a reminder to come in fasting as previously described.
7. Visit #3 (End of the 4-week intervention period). The researcher or GRA will meet the subject in a private room located on the university campus.
  - a. The research or GRA (both are registered nurses) will obtain

- i. Fasting serum blood glucose and plasma insulin levels which will be used to calculate HOMA-IR (as previously described).
  - ii. Dietary Screener questionnaire
  - iii. Baecke physical activity questionnaire
  - iv. Meal Timing questionnaire
  - v. Perceived Stress Scale
  - vi. Height and weight as previously described
  - vii. Subject body fat analysis (using a hand-held, non-invasive calibrated scale) (Omron Body Logic Pro, Omron Healthcare, Inc., Vernon Hills, IL)
  - viii. Both groups will be given the Sleep Hygiene Index questionnaire
  - ix. The Control group will also be given the Safety Practices questionnaire.
  - x. Actigraphy data will be downloaded and actigraph and sleep diary will be returned to researcher.
  - xi. Lastly, an exit interview will be conducted to provide the researcher information on areas that can be improved in the study.
- b. At the end of Visit #3, all subjects will receive \$30, a certificate of appreciation and the control group will also receive sleep hygiene pamphlet (same as one given to intervention group)
- c. All subjects will be given the following information: The following are recommendations from the American Diabetes Association to promote a healthy lifestyle (<http://www.diabetes.org/are-you-at-risk/lower-your-risk/>) and the suggestion made to follow up with a physician.
- d. The researcher will clean the actigraph with antiseptic alcohol-based solution wipes.
- 8. After serum blood values are analyzed, all subjects will be sent a letter with their glucose, insulin, and HOMA-IR results along with a description of these values and recommendation for physician follow up.
- 9. Subjects in the control group will be given the opportunity to receive the sleep education that was provided to the intervention group.

